
To evaluate the objective response rate (ORR) per BICR in all randomized participants.
	
The second secondary endpoint is to describe ORR per BICR in all randomized participants. ORR is defined as the proportion of randomized participants who achieve a best response of complete response (CR) or partial response (PR) using the RECIST 1.1 criteria. Best overall response (BOR) is defined as the best response designation recorded between the date of randomization and the date of objectively documented progression per RECIST 1.1 or the date of subsequent therapy (including tumor-directed radiotherapy and tumor-directed surgery), whichever occurs first. For participants without document progression or subsequent therapy, all available response designations will contribute to the BOR assessment. Duration of response (DOR) is defined as the time between the date of first confirmed documented response (CR or PR) to the date of first documented tumor progression (per RECIST 1.1) or death due to any cause, whichever occurs first. Participants who neither progress nor die will be censored on the date of their last tumor assessment. Responders who started anti-cancer therapy without a prior reported progression will be censored on the date of their last evaluable tumor assessment prior to the initiation of first subsequent anti-cancer therapy. Time to response (TTR) is defined as the time from randomization to the date of the first confirmed documented response (CR or PR), as assessed by BICR. DOR and TTR will be evaluated for responders (CR or PR) only.

Table 4-1: Objectives and Endpoints

Objective	Endpoint
To assess overall safety and tolerability in all treated participants.	As measured by the incidence of adverse events (AEs), serious adverse events (SAEs), AEs leading to discontinuation, deaths, laboratory abnormalities and changes from baseline.
[REDACTED]	[REDACTED]
[REDACTED]	[REDACTED]
[REDACTED]	[REDACTED]
[REDACTED]	[REDACTED]
[REDACTED]	[REDACTED]

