APPENDIX 1 TIME-TO ONSET AND TIME-TO RESOLUTION DEFINITION
AND CONVENTIONS FOR SELECT ADVERSE EVENTS,
IMMUNE-MEDIATED ADVERSE EVENTS AND EVENTS OF
SPECIAL INTEREST 62

[REDACTED]

[REDACTED]

[REDACTED]

LIST OF FIGURES

Figure 2-1: Study Design Schematic 10
Figure 4.1.1-1: PFS Primary Definition 14
Figure 4.1.2-1: PFS Secondary Definition 16

[REDACTED]

[REDACTED]

[REDACTED]

[REDACTED]

Research Hypothesis:

Treatment with nivolumab combined with cabozantinib (doublet regimen) will demonstrate an improvement in PFS per BICR compared to sunitinib monotherapy in subjects with previously untreated mRCC.

Schedule of Analyses:

This study will be monitored by an independent Data Monitoring Committee (DMC). Details are specified in the DMC charter.

The PFS analysis will occur after approximately 9-10 months minimum follow-up on all randomized subjects, which will be triggered by approximately 350 events from Arm A (nivolumab combined with cabozantinib; doublet regimen) and Arm C (sunitinib).

Two interim analyses of OS are planned. The first interim analysis is planned at the time of final PFS analysis and expected after observing 165 deaths among the randomized subjects in Arm A and Arm C (65% of the targeted OS events for final analysis). The second interim analysis is expected after observing 211 deaths among the randomized subjects in Arm A and Arm C (83% of targeted OS events needed for final analysis). The final analysis of OS is expected after observing 211 deaths among the randomized subjects in Arm A and Arm C.

The final PFS analysis will not occur prior to these conditions being met:

- at least 8 months minimum follow-up on all randomized subjects;
- at least 283 PFS events, which provide at least 90% power to detect a HR of 0.68 for PFS of Arm A versus Arm C; and
- at least 149 OS events, which provide 66% power if the observed HR for OS was 0.60.

The expected PFS analysis will occur at approximately 29 months from FPFV. The second interim and final analyses of OS are expected to occur approximately 34 months and 40 months from FPFV.

Secondary endpoints (including both efficacy endpoints OS and ORR) will be analyzed at the time of the final analysis of PFS based on a hierarchical testing strategy. In the event that the interim analysis for superiority of overall survival is positive, final (CSR) analyses will be performed prior to achieving 254 deaths; additional details can be found in [section 7.5.7](#).

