If the formal analysis of PFS among all randomized subjects is statistically significant, the formal interim analysis of OS among all randomized subjects will be tested, as per hierarchical testing procedure. If the formal analysis of OS (interim or final, whichever occurs first) among all randomized subjects is statistically significant, then formal analysis of ORR among all randomized subjects will be tested, as per hierarchical testing procedure. The formal ORR analyses specified in the SAP supersede those specified in the protocol.

Sample Size Computation for Secondary OS Endpoint

The secondary endpoint of OS in all randomized subjects specifies the comparison of Arm A versus Arm C. Among all randomized subjects, approximately 254 events (ie, deaths) in Arm A and Arm C provides at least 80% power to detect a HR of 0.70 for OS of Arm A and Arm C with an overall type 1 error of 0.05 (two-sided) for each test. The HR of 0.70 corresponds to a 43% increase in the median OS, assuming a median OS of 47.1 months for Arm A and 33 months for Arm C.

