7 STATISTICAL ANALYSES

7.1 General Methods

Unless otherwise noted, discrete variables will be tabulated by the frequency and proportion of subjects falling into each category, grouped by treatment. Percentages given in these tables will be rounded to the first decimal and, therefore, may not always sum to 100%. Percentages less than 0.1 will be indicated as '< 0.1'. Continuous variables will be summarized by treatment group using the mean, standard deviation, median, minimum, and maximum values.

Time-to-event variables (e.g. time-to resolution) will be analyzed using the Kaplan-Meier technique. When specified, the median will be reported along with 95% CI using Brookmeyer and Crowley method⁵ (using log-log transformation for constructing the confidence intervals⁶).

Unless otherwise specified, the stratified log-rank test will be performed to test the comparison between time to event distributions. Unless otherwise specified, the stratified hazard ratio between 2 groups along with CI will be obtained by fitting a stratified Cox model with the group variable as a unique covariate.

Confidence intervals for binomial proportions will be derived using the Clopper-Pearson method.⁷ The unweighted difference in ORRs between the two treatment arms and corresponding asymptotic 95% CI will be estimated using a Newcombe method.⁸

P-values from sensitivity analyses for efficacy endpoints are for descriptive purpose only and there will be no multiplicity adjustment for these analyses.

The conventions to be used for imputing missing and partial dates for analyses requiring dates are described in [Section 8](#).

Note that, the outputs will present Arm A, Arm B, and Arm C in the following way:

- All analysis specified in [Section 7.3](#) and [7.4](#) will present A, B, and C together.
- For purposes of efficacy analyses, all randomized subjects in Arm A and Arm C will be tabulated and presented in the same table. A few separate efficacy summary tables will be generated for those subjects randomized to Arm B, which will be specified in the corresponding sections.
- For purposes of safety analyses, all treated subjects in Arm A and Arm C will be tabulated and presented in the same table. A few separate safety summary tables will be generated for those subjects treated in Arm B, which will be specified in the corresponding sections.
- Summaries of outcome research and biomarker data will be tabulated on the Arm A and C subjects only.

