7.5 Efficacy

Analyses in this section will be tabulated for all randomized subjects in Arm A and Arm C, unless otherwise specified. A few separate efficacy summary tables will be generated for those subjects who randomized to Arm B prior to Revised Protocol 01, which is specified in the relevant subsections below.

Principal analyses of progression free survival (PFS) and objective response rate (ORR) will be based on the Blinded Independent Central Review (BICR) evaluation, unless noted otherwise.

Analyses in this section will be tabulated for all randomized subjects by treatment group as randomized, unless otherwise specified.

Unless stated otherwise, whenever a stratified analysis is specified, the following stratifications factors (recorded at randomization as per IRT) will be used:

- IMDC Prognostic Score: 0 versus 1-2 versus 3-6
- Region: US/Canada/W Europe/N Europe versus ROW
- PD-L1 tumor expression: $\geq 1\%$ versus $< 1\%$ or indeterminate

The key secondary objective Overall Survival among all randomized subjects will be tested after conducting the primary objective analyses of PFS on all randomized subjects. For assessing this secondary objective of this study, a hierarchical testing procedure¹⁰ will be used so that the overall experiment-wise Type I error rate is two-sided 0.05.

The secondary objective of ORR among all randomized subjects will be tested after conducting the key secondary objective analyses of OS on all randomized subjects, per a hierarchical testing procedure so that the overall experiment-wise Type I error rate is two-sided 0.05. Note that the formal ORR analysis specified in the SAP supersede those specified in the protocol.

Confidence intervals (CI) for primary and secondary endpoint analyses included in hierarchy will be based on nominal significance level adjusted for primary endpoints and interim analyses to preserve overall type one error rate.

Alpha (α) for the CI will be the same as nominal significance level for hypothesis testing. CIs for other endpoints will be at the two-sided 95% level. All p-values reported will be two-sided. P-values will be rounded to the fourth decimal place. Point estimates and confidence bounds for efficacy variables will be rounded to the second decimal place.

A by-subject listing of efficacy results will be presented including treatment group, treatment duration, BICR progression date, overall survival, death date, etc.

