7.5.8 Analysis of Objective Response Rate

One of the secondary objectives of the study is to evaluate the objective response rate in all randomized subjects in Arm A and Arm C. All the analyses outlined in this section are specified for the all randomized subjects population in Arm A and Arm C, unless otherwise specified. If the formal analysis of OS among all randomized subjects is statistically significant, the formal analysis of ORR among all randomized subjects will be tested, as per hierarchical testing procedure. Note that the formal ORR analysis specified in the SAP supersede those specified in the protocol.

The number and percentage of subjects in each category of BOR per BICR (complete response [CR], partial response [PR], stable disease [SD], progressive disease [PD], or unable to determine [UTD]) will be presented, by treatment group. Estimates of response rate, along with its exact two-sided 95% CI by Clopper and Pearson¹⁵ will be presented, by treatment group.

Similar analyses will be repeated based on the investigator's assessment of ORR. A cross tabulation of BICR best response versus the investigator best response will be presented, by treatment group and by response categories. Concordance Rate of Responders will be computed as the frequency with which investigator and BICR agree on classification of a subject as responder vs. non responder/UTD as a proportion of the total number of randomized subjects assessed by both the investigator and BICR.

The following subject-level graphics will also be provided:

- For the responders only, time courses of the following events of interest will be graphically displayed: tumor response, progression, last dose received, and death.

- For response evaluable subjects (randomized subjects with baseline and at least one on-study tumor assessment),
 - A bar plot showing the best % reduction from baseline in sum of diameter of target lesions based on BICR assessment for each subject will be produced (excluding assessments after PD and assessments after start of subsequent anti-cancer therapy).
 - A plot of individual time course of tumor burden change per BICR assessment will be produced.

A by-subject listing of best overall response will be presented including treatment group, best overall response per BICR and dates of CR/PR/progression.

A by-subject listing of per time point tumor response per BICR will be presented.

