10 DOCUMENT HISTORY

Table 10-1: Document History

Version Number		Description
1		Original issue
2		Employ hierarchical strategy to ORR after PFS and OS. [REDACTED]. Wording of cabozantinib dose delay and dose reductions are cleaned.

APPENDIX 1 TIME-TO ONSET AND TIME-TO RESOLUTION DEFINITION AND CONVENTIONS FOR SELECT ADVERSE EVENTS, IMMUNE-MEDIATED ADVERSE EVENTS AND EVENTS OF SPECIAL INTEREST

Time-to onset definition

Time-to onset of AE (any grade) for a specific category is defined as the time between the day of the first dose of study treatment and the onset date of the earliest AE (of any grade) in this category.

The time-to onset of AE (grade 3-5) for a specific category is defined similarly with an onset date corresponding to a grade 3-5 AE.

Time-to onset of drug-related AE (any grade or grade 3-5) for a specific category is defined similarly but restricted to drug-related AE.

Time-to onset for a specific subcategory is defined similarly but restricted to event of this subcategory.

Time-to resolution definition

In order to derive the time-to resolution, overlapping or contiguous AEs within a specific category or subcategory will be collapsed into what will be termed “clustered” AEs. For example, if a subject (without pre-treatment AE) experienced an AE from 1st to 5th January, another AE (with different PT but within same category) from 6th to 11th January and same AE from 10th to 12th January, these will be collapsed into one clustered AE from 1st to 12th January.

Key derivation steps for each type of clustered AEs is summarized as follows:

- For any grade AE: Collapse any on-treatment AE from the same category

- For drug-related any grade AE: Collapse any on-treatment drug-related AE from the same category
- For grade 3-5 AE: Collapse any on-treatment AE from the same category. Resolution will be based on the onset date of the earliest grade 3-5 records (if no grade 3-5 record, clustered AE is excluded)
- For drug-related grade 3-5 AE: Collapse any on-treatment drug-related AE from the same category. Resolution will be based on the onset date of the earliest grade 3-5 records (if no grade 3-5 record, clustered AE is excluded)

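### Optional, low-cost improvement: name the ORR test in SAP 7.5.8 and stratify it by the three IRT factors already used for randomization, PFS and OS

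*SAP*

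**What the plan says.** The protocol treats ORR as descriptive. In Section 4, Table 4-1: "The second secondary endpoint is to describe ORR per BICR in all randomized participants".

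The SAP changes that. Its document history (Section 10) records for version 2: "Employ hierarchical strategy to ORR after PFS and OS". The opening Schedule of Analyses says that the secondary endpoints, OS and ORR, "will be analyzed at the time of the final analysis of PFS based on a hierarchical testing strategy". Section 5 says that once OS is significant, "then formal analysis of ORR among all randomized subjects will be tested", and that the SAP overrides the protocol on this. Section 7.5 orders the ORR test after OS, "per a hierarchical testing procedure so that the overall experiment-wise Type I error rate is two-sided 0.05". Section 7.5.8 repeats that "the formal analysis of ORR among all randomized subjects will be tested, as per hierarchical testing procedure".

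The visible analysis methods for ORR are:

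- SAP 7.1, between arms: "The unweighted difference in ORRs between the two treatment arms and corresponding asymptotic 95% CI will be estimated using a Newcombe method".
- SAP 7.5.8, within each arm: Clopper-Pearson exact intervals. No between-arm test or stratification is named there.

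The general rules do not fill the gap. The stratified defaults in SAP 7.1 are the log-rank test and Cox model, so they cover time-to-event endpoints only. The factor list in SAP 7.5 applies "whenever a stratified analysis is specified, the following stratifications factors (recorded at randomization as per IRT) will be used", and no stratified analysis of ORR is specified in the visible text.

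Randomization uses permuted blocks within strata of IMDC score, region and PD-L1 (SAP 2.1). PFS (SAP 7.5.1) and OS (SAP 7.5.4) are tested by log-rank tests stratified on those factors.

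**The concern.** ORR is the only member of the hierarchy whose visible analysis leaves out the randomization factors, and the only one with no named test. Two things follow.

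First, an endpoint that carries a type I error claim should have its test fixed in writing before database lock. An interval for a difference implies a decision rule but does not state one.

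Second, stratified randomization balances the arms on the three factors. If those factors predict response, the true sampling variance of the difference in ORRs is smaller than the unstratified formula assumes. The interval is then somewhat too wide and the implied test rejects too rarely. At stake is a small amount of power on a third-ranked endpoint, and only if PFS and OS have both succeeded.

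**Working it through.** **The plan's own figures.** The documents give no ORR rate, power or sample size, so there is no ORR figure to reproduce. The sizing that is given does reproduce. For PFS, 4(1.960 + 1.645)² / (ln 0.68)² = 349.5, matching 350 events for 95% power.

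**Inputs from the documents.** 638 subjects, 319 per arm, 1:1; favorable risk about 25%; 3 × 2 × 2 = 12 strata; two-sided 0.05.

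**Assumed inputs (set A).** IMDC 25/58/17%, PD-L1 ≥ 1% in 25%, region 50/50, blocks of 4, control ORR 30% (20% and 40% also run), common odds ratio 1.5 or 2.0. Log-odds effects on response are:

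- moderate: IMDC +0.5/0/−0.7, PD-L1 +0.4, region +0.3 (control ORR 14 to 51% across strata);
- strong: IMDC +0.9/0/−1.3, PD-L1 +0.6, region +0.5 (6 to 65%).

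The decision rule for the SAP method, that the Newcombe interval excludes 0, is also an assumption.

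**Closed-form check at control ORR 30%, odds ratio 1.5.** Let w be the stratum shares, p_C and p_A the stratum response rates, P_C and P_A their averages, and d = P_A − P_C.

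- Unstratified SE: U = √{[P_C(1−P_C) + P_A(1−P_A)]/319}
- Actual SE under stratified randomization: S = √{Σw[p_C(1−p_C) + p_A(1−p_A)]/319}
- Power, unstratified rule: Φ[(d − 1.96U)/S]
- Power, stratified rule: Φ(d/S − 1.96)

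| Factors | d (points) | U | S | Unstratified power | Stratified power |
|---|---|---|---|---|---|
| Not prognostic | 9.130 | 3.748 | 3.748 | 68.3% | 68.3% |
| Moderate | 8.744 | 3.745 | 3.669 | 64.9% | 66.4% |
| Strong | 8.121 | 3.739 | 3.537 | 58.9% | 63.2% |

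For the strong row, (8.121 − 1.96 × 3.739)/3.537 = 0.224 gives 58.9%, and 8.121/3.537 − 1.96 = 0.336 gives 63.2%.

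Under the null, S²/U² is 0.963 (moderate) and 0.901 (strong). The type I error of the unstratified rule is 2Φ(−1.96/√0.963) = 4.6% and 2Φ(−1.96/√0.901) = 3.9%.

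**Simulation, set A (100,000 trials per cell).** Newcombe versus CMH without continuity correction:

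- Power at control ORR 30%, odds ratio 1.5: 67.9% vs 67.8% (not prognostic), 64.7% vs 66.1% (moderate), 58.9% vs 63.1% (strong).
- Across control ORR 20 to 40%, the CMH gain at odds ratio 1.5 is 1.2 to 1.4 points (moderate) and 3.5 to 4.2 (strong). At odds ratio 2.0 it is 0.1 to 0.2 and 0.5 to 1.0. With non-prognostic factors CMH is 0.0 to 0.3 points worse.
- Type I error with strong factors: 3.8 to 4.1% vs 5.0 to 5.1%.
- Interval half-width at control ORR 30%, odds ratio 1.5, Newcombe vs Mantel-Haenszel with Sato variance: 7.30 vs 7.34 points (not prognostic), 7.29 vs 7.18 (moderate), 7.28 vs 6.93 (strong).
- Other stratum splits, IMDC as the only prognostic factor, or odds ratios varying by IMDC group: gains of 0.9 to 1.9 (moderate) and 3.1 to 6.0 (strong).

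**Simulation, set B (20,000 trials per cell).** Intermediate/poor 55/20%, PD-L1 ≥ 1% in 27%, control ORR 25% or 35%, difference 10 points:

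- Gain: about 0 (not prognostic), 0.2 to 0.3 (mild), 0.9 to 1.2 (moderate), 2.6 to 3.4 (strong).
- The sampling SDs of the stratified and unstratified differences agree in every scenario, for example 0.0355 and 0.0355 (moderate, control ORR 25%).
- At 30% vs 50% with moderate factors, power is 99.94% vs 99.96%.

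**The case against.** The strongest reply is that this is a matter of preference. The unweighted difference is valid, matches the tabulated rates, and breaks no rule in the SAP. That stands, and it is why the priority is optional.

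Several further objections also stand:

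- **The gain is conditional.** The documents never say that the factors predict response. The protocol's introduction ties the IMDC groups to survival. With mild effects the gain is 0.2 to 0.3 points, and with none CMH is marginally worse.
- **The comparator is inferred.** SAP 7.5 ties the interval's level to the test's level, but no text makes the Newcombe interval the test.
- **The setting is narrow.** ORR is tested only after PFS and OS succeed. OS is designed for 80% power, so under the design alternatives ORR is reached at most about 80% of the time.
- **Text is redacted.** The SAP contents list blacks out the entry between 7.5.8 and 7.5.10, and text directly after the ORR change in the document history is also blacked out. The protocol's abbreviation list defines CMH although no visible text uses it. That list looks partly generic, so this proves nothing, but a stratified ORR test may already exist.

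A reader might infer that the unstratified comparison inflates the type I error. The calculations show the opposite: it is at or near 5%, and below it when the factors matter. A reader might also infer that stratifying makes the estimate more precise, as if subjects had been added. It does not. Randomization has already removed that variability, and CMH only stops the standard error from overstating it.

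**Conclusion.** The point holds as a low-cost improvement, not as an error. The visible SAP tests ORR formally, names no test statistic, and gives only an unstratified between-arm method, while randomization, PFS and OS use three factors forming 12 strata.

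For a modest effect (odds ratio about 1.5, or 10 points), naming a CMH test on those factors would gain about 0 points of power if they are not prognostic, with at most about 0.3 lost. It would gain about 1 point if they are moderately prognostic and about 3 to 4 if strongly so. For large effects the gain is 1 point or less. With strong factors the type I error is about 4% unstratified against 5% for CMH.

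Every ORR rate, stratum effect, PD-L1 and region split, and the block size is assumed, as is the Newcombe decision rule. The documents do not support an unconditional claim that CMH is more efficient. Nor do they show that the sponsor has no stratified ORR test, because part of the efficacy section cannot be seen.

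**What to change.** In SAP 7.5.8, state the following:

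- ORR per BICR is tested with a two-sided CMH test stratified by IMDC score, region and PD-L1 per IRT, at the hierarchy's 0.05 level after OS.
- The Mantel-Haenszel weighted difference is reported with a stratified interval at the same level, for example with the Sato variance.
- The unweighted Newcombe difference is kept as supportive.

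If a redacted section already specifies a stratified ORR test, confirm it and add a cross-reference from 7.5.8.

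The cost is one or two sentences and a standard procedure; the strata are already in IRT. There are two downsides.

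- **Small strata.** Under set A the smallest two expect 638 × 0.17 × 0.25 × 0.5 = 13.6 subjects each, and the next two 638 × 0.25 × 0.25 × 0.5 = 19.9. No pooling rule is needed, because a stratum with an empty arm gets zero weight. This occurred in at most about 0.01% of trials simulated with near-even allocation. In a skewed mix with a smallest expected stratum of about 3 (638 × 0.10 × 0.15 × 0.30), CMH still lost almost nothing (75.7% vs 75.8% power).
- **Presentation.** The weighted difference does not exactly equal the difference of the tabulated rates. In simulation the gap averaged 0.06 to 0.18 points and reached at most 1.2.
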